#### **14.1.2 Study Drug Supply**

Edaravone multi-use bottles will be packaged, labeled, and released according to good manufacturing practices. All labeling will comply with applicable regulatory requirements. The Sponsor will provide all required release documentation for the finished product before it is dispatched.

The Sponsor will provide the necessary documentation, such as a Certificate of Analysis or Quality Control release document.

#### **14.1.3 Formulation, Packaging, and Labeling**

Documentation for edaravone bottles will include, but may not be limited to, the following information:

- Receipt date
- Description of drug package, and drug product
- Lot/Batch/Code/other
- Expiration and Manufacturing dates
- Investigational New Drug (IND) number
- Certificate of Compliance

#### **14.1.4 Shipping, Receipt, Handling and Storage**

Drug accountability will be noted by the study monitor during site visits and at the completion of the study. Subjects will be asked to return all unused study drug and packaging at each on site clinic visit, at the end of the study or at the time of study treatment discontinuation.

The investigational product should be stored at 2°C to 8°C (36°F to 46°F) in its original carton to protect from light. Investigational product should not be frozen. Sites will be required to monitor temperature of the investigational product while on-site.

Subjects will be instructed to store the medication under refrigerated conditions and protected from light, according to the investigational medicinal product (IMP) clinical label.

#### **14.1.5 Dispensing**

Per interactive web response system (IWRS) instructions (at Visit 1 and each clinic visit), the Pharmacist/trained designee, or other qualified drug vendor, will provide the subject with the appropriate number of bottles of edaravone suspension for the administration treatment period. A record of the study medication dispensed to each subject will be maintained by the Investigator or designee in a Drug Accountability Log.

#### **14.1.6 Study Medication Accountability**

The Pharmacist/trained designee must maintain an accurate record of the study medication shipment. During the study, the Pharmacist/trained designee will record the quantities of edaravone bottles dispensed on a Drug Accountability Log. The accountability (drug reconciliation) will be noted by the monitor during site visits and at the completion of the study. Edaravone bottles are to be used only for this Protocol and not for any other purposes.

#### **14.1.7 Disposal and Destruction**

At study closeout, and as appropriate during the course of the study, the Investigator will return all used and unused study drug, packaging, and a copy of the completed Drug Accountability Log to the Sponsor's designated monitor or to the address provided in the Investigator Binder at each site.

The study medication supply may be destroyed at the designated Sponsor facility or third party, as appropriate. Sites with documented drug destruction procedures and facilities may destroy drug on site after obtaining sponsor approval.

### **14.2 Dosing of Oral Edaravone**

All subjects enrolled will receive 105 mg of oral edaravone, once daily, as specified in the protocol (daily dosing for 10 days out of 14-day periods, followed by 14-day

drug-free periods. Treatment cycles are every 4 weeks), with the appropriate days off-treatment in each cycle. Treatment cycles will occur every 28 days.

The dose of edaravone should be taken after an overnight fast and subjects must continue to fast at least 1 to 2 hours postdose before the next meal (e.g., breakfast).

A description of the oral edaravone and study medication dispensed is provided in Table 3.

**Table 3: Investigational Product**

Product Name	Edaravone
Dosage Form	Oral suspension
Unit Dose	105 mg
Route of Administration	Oral/ PEG/RIG tube
Physical Description	Aqueous viscous suspension
Manufacturer	Mitsubishi Tanabe Pharma Corporation

#### **14.3 Treatment Compliance**

The prescribed dosage, timing, and mode of administration of study medication may not be changed except for PEG/RIG dosing as the subject's disease progresses. Drug compliance should be assessed on a per cycle basis by site staff either via phone calls or during their on-site study visits to assess their dosing compliance. Subjects will be asked questions regarding the compliance, and any departures from the intended regimen must be recorded in the eCRF. Study drug accountability and treatment compliance will be documented throughout the study period.

Subjects will be asked to return all unused medication including empty and partially used medication. Study medication dispensed at the previous visit will be collected by the site and compliance will be assessed by counting the returned study medication bottles.

Non-compliance is defined as taking <80% or >120% of study medication during evaluation periods (visit to visit).

#### **14.4 Subject Identification**

Each subject will continue to be identified by the unique Subject Identifier that was assigned to them at the screening visit of study MT-1186-A01.

The Subject Identifier will be used to reference the subject during the whole duration of the study. The Subject Identifier will be documented in the subject's source documents. The Subject Identifier will be recorded on study medication labels and other documentation.

A list identifying the subjects by their unique Subject Identifier will be kept in the Investigator Site File.

#### **14.5 Procedures for Assigning Subjects to Treatment Groups**

This is an open-label study. Therefore, no randomization or blinding is applicable.

#### **14.6 Dose Adjustment Criteria**

Dose adjustments of oral edaravone will not be allowed.

## **15 ADVERSE EVENT MANAGEMENT**

All AEs and SAEs will be recorded in the source documents. All AEs and SAEs that occur from the time written ICF is obtained until the end of the Safety Follow-up Period will be recorded in the eCRF. Even if an AE is assessed by the Investigator as not related to IMP, its occurrence must be recorded in the source documents and eCRF. AEs will be classified as ‘treatment-emergent’ if they arise following the administration of IMP or if a predose AE increases in severity following dosing.

At each study visit, after the subject has had an opportunity to spontaneously mention any problems, the Investigator should inquire about the occurrence of AEs. The questioning should be open-ended and non-leading.

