d. Physical examination:

1. A full physical examination will consist of an assessment of major body parts and systems: abdominal, cardiovascular, general appearance, head, eyes, ears/nose/throat, lymph nodes, musculoskeletal, neck, neurological, dermatological, respiratory, and other.
2. Routine physical examination will include abdominal, cardiovascular, general appearance, respiratory, neurological, and other.

e. A 12-lead ECG will be performed after the subject has rested for at least 5 minutes in a supine position. The ECG must include the following measurements: R wave to R wave (RR) interval, heart rate, QRS, QT, QTcB, and QTcF. The Investigator will perform an overall evaluation of the ECG for safety purposes and the recording will be reported as 'normal', 'abnormal clinically significant (CS)', or 'abnormal not clinically significant (NCS)'. Abnormalities of clinical significance will be reported as AEs.

f. Events are time to death, tracheostomy, or permanent assisted mechanical ventilation (> 23 hours/day).

g. To include: Red blood cell count, hemoglobin, hematocrit value, white blood cell count including differential, and platelet count

- h. To include: albumin, total protein, aspartate aminotransferase (AST), alanine aminotransferase (ALT), lactate dehydrogenase (LDH), alkaline phosphatase (ALP), total bilirubin, direct bilirubin, CK, total cholesterol, triglycerides, BUN, bicarbonate, serum glucose, serum creatinine level, uric acid, sodium (Na), potassium (K), chloride, and calcium (Ca). Note: albumin will be included in the chemistry profile for Weeks 24, 48, 72 and 96 only. The Day 1/screening assessment will not include albumin as it was not collected as part of Study MT-1186-A01 chemistry profile.
  - i. To include protein, glucose, occult blood, urobilinogen, white blood cells, and bilirubin.
  - j. Subjects will receive oral edaravone at a dose of 105 mg administered once daily for 10 days out of a 14-day period, followed by a 14-day drug- free period for 96 weeks of treatment or until the drug is commercially available in that country. The dose of edaravone should be taken following an overnight fast and at least 1 to 2 hours before the morning meal.
  - k. Drug compliance should be assessed on a per cycle basis by site staff via phone calls or during the in-clinic visits.

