#### **10.1.2 End of Treatment**

The EOT visit will occur at Week 94, when the drug is commercially available in that country, or in the event the Sponsor discontinues the study.

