#### **10.1.3 Safety Follow-up Period/End of Study/Early Termination**

A safety follow-up period (e.g., Visit 9, Week 96 [ $\pm 7$  days]) will be conducted for subjects who complete the open-label treatment period, per the Schedule of Assessments (Table 1).

For subjects who terminate early from the study, assessments should be performed per the Schedule of Assessments (Table 1) within 7 days of study discontinuation.

Any unresolved AE or SAE will be followed up according to Section 15.8.

In the event that a subject elects not to return to the clinical site for the ET Visit, the Investigator must make every effort to contact the subject to review all AEs. In the event that a subject drops out of the study at any time, the reason for discontinuation must be fully documented in the source documents and the eCRF. The Investigator site personnel will document the AEs and any other assessments in the source documents and will make every effort to complete all required ET assessments.

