### **13.2 Time to Death, Tracheostomy, or Permanent Assisted Mechanical Ventilation**

On Day 1 of treatment with oral edaravone through EOT/ET, the Investigator (or subinvestigator) will investigate the presence or absence of the following events:

- Time (days) to death
- Time (days) to tracheostomy
- Time (days) to permanent assisted mechanical ventilation ( $\geq 23$  hours/day)

If any of the events are present, the following will be recorded in the eCRF: the date of the event and end of study date will be investigated. If the subject discontinues the study drug, study sites must follow-up with phone calls at Weeks 24, 48, 72, and 94 to determine if any of the above events have occurred (refer to Table 1). The evaluation results, together with the dates of the evaluation, will be recorded in the eCRF.

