4. STUDY DESIGN

4.1. Study Design

[figure not shown]
This is a Phase 3, international, multi-center, open-label, long-term extension study following the MT-1186-A01 study. The study will evaluate the safety of edaravone at a dose of 105 mg administered once daily for 10 days out of 14, followed by a 14-day drug-free period up to 96 weeks of treatment or until the drug is commercially available in that country.

Subjects who complete treatment in Study MT-1186-A01 and meet eligibility criteria will be enrolled into this open-label treatment study (MT-1186-A03) and will continue to receive 105 mg of edaravone once daily following an overnight fast, and subjects must continue to fast at least 1 to 2 hours before the next meal (e.g., breakfast). Treatment cycles will occur every 28 days (10 days on study drug out of a 14-day period, followed by 14 days off study drug).

Concomitant use of riluzole will be permitted during the study. Subjects who discontinue from the study before Week 96 will complete the procedures listed in Week 96 within 7 days of discontinuation as End of Study (EOS) procedures.

Further details can be found in the Study Schema (Figure 1: Study Schema). The schedules of assessment for each country specific (Germany and France) are referred to each country specific protocol.

Figure 1: Study Schema

Abbreviation: ET = early termination; EOT = end-of-treatment; EOS = end-of-study.

a. Subjects will receive oral edaravone at a dose of 105 mg administered once daily for 10 days out of a 14-day period, followed by a 14-day drug-free period. The dose of edaravone should be taken following an overnight fast and at least 1 to 2 hours before the morning meal.

b. Day 1 is equal to the Week 48 visit of the MT-1186-A01 study.

Table 1: Schedule of Activities for Global

| Assessment | Week (window) | Open-label Treatment Period | | | | | | Safety Follow-up Period ^a |
|--|---------------|---|--------------|--------------|--------------|--------------|------------------------------------|--------------------------------------|
| | | Day 1 (Based upon Week 48 procedures from 1186-A01) | 12 (± 7D) | 24 (± 7D) | 36 (± 7D) | 48 (± 7D) | 60 Telephone Visit (± 7D) | |
| Cycle | 1 | 4 | 7 | 10 | 13 | 16 | 19 | 24 |
| Visit | 1 | 2 | 3 | 4 | 5 | 6 | 7 | 9 |
| Informed consent | X | | | | | | | |
| Eligibility criteria | X | | | | | | | |
| Demographics ^b | X | | | | | | | |
| Vital signs ^c | X | X | X | X | X | X | X | X |

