The numbers and proportions of subjects with TEAEs will be calculated by Cycle of treatment and by SOC and PT. Cycles will be categorized into grouping of: Cycle 1-6, Cycle 7-12, Cycle 13-18 and Cycle 19-24.

For each of the summaries, multiple occurrences of the same event within a subject will be counted once in the summaries by SOC and PT; multiple occurrences of the same event within a subject will be counted once in the maximum severity category (severe > moderate > mild) and/or maximum study drug relationship category (reasonable possibility / no reasonable possibility). If severity or relationship is found to be missing the most severe occurrence will be imputed for that particular summary.

In the analysis of TEAEs by Cycle, reoccurrences of TEAE's per subject can be shown multiple times if occurred in different cycles categories. The TEAEs occurred at follow up period of subjects who completed the study will be categorized Cycle 19-24.

Subject's data listings will be provided for: TEAEs, TESAEs, TEAE leading to discontinuation of study drug and Death

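### No scheduled visit falls between Weeks 72 and 94 and AE enquiry is required only at visits, so the Cycle 19-24 column of the by-cycle TEAE table may under-show non-serious events

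*Protocol*

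**What the plan says.** **Schedule.** The cycle row of the schedule of activities (SAP Section 4.1, Table 1; the Protocol's Table 1 corresponds) reads "Cycle | 1 | 4 | 7 | 10 | 13 | 16 | 19 | 24". Protocol 10.1.2 states "The EOT visit will occur at Week 94", and Protocol 10.1.3 has "A safety follow-up period (e.g., Visit 9, Week 96" as the follow-up visit.

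**AE enquiry.** Protocol Section 15 instructs: "At each study visit, after the subject has had an opportunity to spontaneously mention any problems, the Investigator should inquire about the occurrence of AEs". No other instruction in the documents says when to ask about AEs. The same section requires every AE from consent to the end of safety follow-up to be recorded, and Section 15.7 requires SAEs to be reported within 24 hours of the investigator learning of them.

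**Contact between visits.** Protocol Table 1, footnote k: "Drug compliance should be assessed on a per cycle basis by site staff via phone calls or during the in-clinic visits". Section 14.3 repeats it ("Drug compliance should be assessed on a per cycle basis by site staff either via phone calls or during their on-site study visits") and describes the content as questions about compliance. For subjects who have stopped study drug, Section 13.2 says "study sites must follow-up with phone calls at Weeks 24, 48, 72, and 94"; those calls ask about death, tracheostomy and permanent ventilation.

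**Analysis.** SAP 9.3.1, for TEAEs by cycle: "Cycles will be categorized into grouping of: Cycle 1-6, Cycle 7-12, Cycle 13-18 and Cycle 19-24". The table gives numbers and proportions of subjects by SOC and PT. Completers' follow-up events go into the last group. The SAP does not mention that visits are spaced differently in that group.

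**The concern.** The primary objective is long-term safety and there is no control arm, so the pattern of TEAEs over successive cycle groups is one of the few internal comparisons the study offers. The group with the longest exposure is also the one in which subjects wait longest before anyone is required to ask them about AEs. If minor events are forgotten or not volunteered, a real late increase could be blunted, or a fall could appear where the true rate was constant. Contact in every cycle is already required during the gap, but the plan does not say that AEs are asked about then, so practice may differ between sites and cannot be verified from the plan.

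**Working it through.** **1. Visit weeks and gaps.** With Day = 7 × week + 1 and cycle = floor(7 × week / 28) + 1, Weeks 0, 12, 24, 36, 48, 60, 72 and 94 give Cycles 1, 4, 7, 10, 13, 16, 19 and 24, which reproduces the plan's cycle row. A Week 84 visit would be Day 589, in Cycle 22, and no Cycle 22 visit is listed. The week header of the table is broken in the text, so Visit 8 at Week 94 is inferred from the cycle row, from Protocol 10.1.2 and from Visit 9 being Week 96.

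Gaps: 12, 12, 12, 12, 12, 12, 22, then 2 weeks. With ±7-day windows, a 12-week gap can be 10 to 14 weeks, and the 22-week gap 20 to 24 if the same window applies at Week 94.

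**2. Look-back.** If onsets are spread evenly, mean look-back is half the gap: 22/2 = 11 weeks against 12/2 = 6. Over the whole last block, including Weeks 94-96, the mean is (22 × 11 + 2 × 1)/24 = 10.2 weeks.

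**3. Number of enquiries.** Cycle 1-6 onsets are asked about at Weeks 12 and 24. Cycle 19-24 (from Day 505, Week 72) onsets are asked about at Weeks 94 and 96. Each block has two enquiries; the spacing differs.

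**4. What a recall loss would do.** The documents give no under-reporting rate, so this is a sensitivity range. Assume the chance of reporting a non-serious event halves every H weeks after onset and that AEs are heard only at visits. Mean capture over a gap of g weeks is

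C(g,H) = (1 − 2^(−g/H)) / (ln 2 × g/H).

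An earlier block has two 12-week gaps and captures C(12,H). The last block has one 22-week and one 2-week gap and captures [22 × C(22,H) + 2 × C(2,H)]/24. Shortfall = 1 − last/earlier.

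For H = 12: C(12) = 0.721, C(22) = 0.566, C(2) = 0.944. Last block = (22 × 0.566 + 2 × 0.944)/24 = 0.598. Shortfall = 1 − 0.598/0.721 = 17%.

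| H (weeks, assumed) | C(12) | C(22) | C(2) | Last block | Shortfall |
|---|---|---|---|---|---|
| 8 | 0.622 | 0.447 | 0.918 | 0.486 | 22% |
| 12 | 0.721 | 0.566 | 0.944 | 0.598 | 17% |
| 26 | 0.856 | 0.757 | 0.974 | 0.775 | 9% |
| 52 | 0.924 | 0.867 | 0.987 | 0.877 | 5% |

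**5. With the AE question at every per-cycle contact.** The longest look-back is about 4 weeks in every block. Cycle starts at Weeks 76, 80, 84, 88 and 92 fall inside the present gap. For H = 12, an earlier block captures C(4) = 0.893, and the last block (20 × 0.893 + 4 × 0.944)/24 = 0.901. Across the four half-lives the blocks then differ by less than 1.5%.

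**The case against.** The best case against the point is that the plan has other routes by which AEs surface. Site staff speak to each subject every cycle and must record departures from the regimen, so AEs that cause missed doses are likely to come up. An AE volunteered on such a call is recordable, because recording is not limited to visits. Unscheduled safety visits exist (Protocol 10.1.4), early leavers are assessed within 7 days, and end of treatment comes sooner where the drug becomes commercially available. SAEs follow their own 24-hour rule. The analysis is descriptive, with no hypothesis test. All of this stands. It limits the problem to non-serious events that are not volunteered, in subjects who stay on study. It does not remove it, because nothing in the plan requires anyone to ask.

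Some stronger readings are tempting but not supported:

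- *Late AEs rest on 22-week recall.* Twenty-two weeks is the maximum between visits. The mean is about 11, and the per-cycle contact may shorten it in practice.
- *The table will show too few late events.* The documents give no reporting rate, and the shortfall rests wholly on the assumed half-life. The model also lets every event fade from onset, whereas one still ongoing at Week 94 needs no recall.
- *The shortfall is 28%, 22%, 12% or 6% at half-lives of 8, 12, 26 or 52 weeks.* Those figures compare a 22-week gap alone with a 12-week gap. The block also contains Weeks 94-96, which lowers them to 22%, 17%, 9% and 5%.
- *Earlier blocks have two enquiries and the last has none until Week 94.* Each block has two, as step 3 shows.
- *The time-to-event endpoint suffers in the same way.* Death, tracheostomy and permanent ventilation are dated hard events, and the latter two require withdrawal (Protocol 9.6), which brings early-termination assessments. The recall argument does not extend to them.

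The France and Germany schedules are in country-specific protocols that the SAP cites but does not reproduce, so they could not be checked.

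**Conclusion.** The point holds in a conditional form. The 22-week gap between scheduled visits, against 12 weeks earlier, is established from the plan's own schedule, and the only instruction to ask about AEs is attached to visits. Followed as written, the plan gives weaker ascertainment of non-serious AEs in Cycles 19-24 than in the other groups. The direction is the same for any recall loss; the size is unknown. The 5% to 22% range assumes exponential loss of recall with a half-life between 52 and 8 weeks, evenly spread onsets, subjects who stay on study, and no AE heard outside visits. It refers to captured events. The table counts each subject once per SOC and PT within a cycle group, so the percentages do not carry over to its cells one for one.

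This is a cheap improvement to the plan, not a flaw that undermines the safety evaluation.

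**What to change.** - **Protocol Section 15 and Table 1, footnote k:** add the existing open-ended, non-leading AE question to the per-cycle compliance contact, in all cycles. Adding it only in Cycles 20 to 23 would tilt the comparison the other way: at an assumed 26-week half-life the last block would capture (20 × 0.949 + 4 × 0.974)/24 = 0.953 against 0.856 earlier, about 11% more.
- **SAP 9.3.1:** state how often AEs were solicited, so that readers of the by-cycle table know the basis of each column.
- **If the change cannot be implemented:** say in SAP 9.3.1 whether AEs were asked about at the per-cycle contacts, and put a note on the Cycle 19-24 column that non-serious AEs may have been collected over up to 22 weeks, against 12 in the other columns.

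Cost: a wording change and a few minutes in contacts already required, with no new visit or staff. The downside is more minor AEs to record.

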### **15.1 Adverse Event**

An AE is any untoward medical occurrence in a subject or clinical investigation subject administered a pharmaceutical product that does not necessarily have a causal relationship with this IMP. An AE can therefore be any unfavorable and unintended sign (including an abnormal laboratory finding, for example), symptom, or disease temporally associated with the use of an IMP, whether or not considered related to the IMP. Instances of aggravation of events (in terms of seriousness) are treated as new AEs.

### **15.2 Serious Adverse Event**

An SAE is defined as any untoward medical occurrence that at any dose:

- Results in death;
- Is life-threatening;
- Requires hospitalization or prolongation of existing hospitalization;
- Results in persistent or significant disability or incapacity;
- Is a congenital anomaly or birth defect;
- Is an important medical event.

Medical and scientific judgement should be exercised in deciding whether an AE is serious and whether expedited reporting is appropriate in other situations, such as important medical events that may not be immediately life-threatening or result in death or hospitalization but may jeopardize the subject or may require medical or surgical intervention to prevent one of the other outcomes listed in the above definition. These should also be considered serious.

Examples of such events are invasive or malignant cancers, intensive treatment in an emergency room or at home for allergic bronchospasm, blood dyscrasias, or convulsions that do not result in hospitalization, or development of drug dependency or drug abuse. These should also usually be considered serious.

The term 'life-threatening' refers to an event/reaction in which the subject was at risk of death at the time of the event/reaction; it does not refer to an event/reaction, which hypothetically might have caused death if it were more severe.

Admission to a hospital as a new inpatient is deemed as meeting this criterion, even when the length of hospital stay was less than 24 hours. Transfer to other departments of the same hospital due to a newly emerged event during the hospitalization (e.g., transfer from the psychiatry ward to the internal medicine ward, from the internal medicine ward to the coronary intensive care unit, or from the neurology ward to the tuberculosis ward) is also counted as hospitalization.

SAEs will be recorded and reported as described in Section 15.7.

